4. SELECTION AND WITHDRAWAL OF PARTICIPANTS

A. INCLUSION CRITERIA

Anyone meeting all of these criteria is eligible for enrollment as study participants:

1. Age 1-65 years of either sex, any race, any ethnicity.
2. Subjects who have completed an immunotherapy trial for peanut allergy within the last 18 months and are unable to tolerate $\geq 300\text{mg}$ of peanut.
3. Written informed consent from patient (if ≥ 18 years) or permission of parent/guardian with participant's assent (if between 7-17)

B. EXCLUSION CRITERIA

Participants who meet any of these criteria are not eligible for enrollment as study participants:

1. History of a severe anaphylactic reaction to peanut, defined as hypoxia, hypotension, or neurologic compromise (cyanosis or $\text{SpO}_2 < 92\%$ at

any stage, hypotension, confusion, collapse, loss of consciousness, or incontinence)

2. Eosinophilic or other inflammatory (e.g. celiac) gastrointestinal disease
3. Severe asthma (2007 NHLBI Criteria Steps 5 or 6 – Appendix 2)
4. Use of β -blockers (oral), angiotensin-converting enzyme (ACE) inhibitors, angiotensin-receptor blockers (ARB) or calcium channel blockers
5. Significant medical condition (e.g., liver, kidney, gastrointestinal, cardiovascular, hematologic, or pulmonary disease) which would put the subject at risk for induction of severe food reactions.
6. Currently participation in an interventional study for peanut allergy.
7. Pregnancy or lactation.

C. PREMATURE WITHDRAWAL CRITERIA

Participants may be prematurely withdrawn from the study if:

1. At any point in the study, the participant elects to withdraw consent from all future study activities.
2. The participant is “lost to follow-up” (i.e., no further follow-up is possible because attempts to reestablish contact with the participant have failed).
3. The participant develops a medical condition that the investigator deems incompatible with participation in the trial. That includes specifically developing Eosinophilic Esophagitis (participants who develop symptoms compatible with Eosinophilic Esophagitis will be referred to a gastroenterologist).
4. Severe atopic dermatitis requiring oral steroids or immunmodulatory agent, or severe asthma; requiring more than daily medium dose inhaled corticosteroids (more than Flovent 440 mcg daily or its equivalent)
5. The use of systemic corticosteroids in the past 30 days.

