5. STUDY DESIGN AND SCHEDULE

A. LOCATION

Visits will be done at the University of North Carolina-Chapel Hill Food Allergy Study Center (FASC), located in the CTRC building. The FASC is equipped as a clinic. In addition to MD and NP coverage, there are 24-hour adult and pediatric rapid response teams in case of emergencies. The study

site is adjacent to the UNC Hospitals Emergency Department where subjects can be transferred for continued monitoring and acute care as needed.

B. DURATION OF ENROLLMENT

The study enrollment duration is for 2 years or until a commercial peanut OIT products is available to participants whichever is sooner.

C. DURATION OF THE STUDY PER PARTICIPANT

Each participant will be in the study for a total of 12 months. There will be three phases in the study: escalation phase for 1 day, build up phase up to 16 weeks, and maintenance phase up to 3 months on peanut OIT followed by 6 months of food equivalent to tolerated peanut protein.

D. STUDY VISITS

Participants will have: an initial study visit (screening), followed by one visit for the escalation phase, followed by visits every 1-2 weeks for the up dosing phase, a visit at the end of peanut OIT treatment at 6 months, a phone interview at 9 months and a final visit at the end of the study at 12 months. The screening visit may be combined with the initial escalation visit.

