1. SCREENING AND BASELINE VISIT

We will perform screening during the initial study visit. We will determine if the patient is still eligible for the study, discuss the study and consent with the patient, perform physical exam and spirometry (participants \geq 7 years old). A blood draw and skin prick test may also be performed.

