We will monitor subjects for the development of eosinophilic esophagitis using Modified Aceves Questionnaire for all of our patients. The questionnaire will be done at screening, then visits 4,6,9,10,11 and 12. The answers in the questionnaire will be scored and those who have a score of 5 or more will be evaluated for possible Eosinophilic Esophagitis and will be referred to gastroenterology

C. RELATIONSHIPS TO PROCEDURE DEFINITIONS

Associated: There is a reasonable possibility that the adverse event may have been caused by the test product and/or procedure. This definition applies to those adverse events that are considered definitely, probably or possibly related to the procedure.

1) Definitely related: An adverse event that follows a temporal sequence from administration of the test product and/or procedure; follows a known response pattern to the test article and/or procedure; and, when appropriate to the protocol, is confirmed by improvement after stopping the test product (and by

reappearance of the reaction after repeat exposure); and cannot be reasonably explained by known characteristics of the subject's clinical state or by other therapies.

2) **Probably related:** An adverse event that follows a reasonable temporal sequence from administration of the test product and/or procedure; follows a known response pattern to the test product and/or procedure, is confirmed by improvement after stopping administration of the test product or stopping the procedure; and cannot be reasonably explained by the known characteristics of the participant's clinical state or other therapies.

3) **Possibly related:** An adverse event that follows a reasonable temporal sequence from administration of the test product and/or procedure and follows a known response pattern to the test product and/or procedure, but could have been produced by the participants' clinical state or by other therapies.

Not associated: An adverse event for which sufficient information exists to indicate that the etiology is not related to the test product and/or therapy.

Unrelated: An adverse event that does not follow a reasonable temporal sequence after administration of the test product and/or procedure; and most likely is explained by the participant's clinical disease state or by other therapies. In addition, no change in a reaction with stopping or restarting the test product or procedure would support an unrelated relationship.

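### A screening EoE score of 5 or more need not be evaluated before the first peanut dose; as a lesser gap, follow-up of a late EoE work-up may stop at 30 days

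*Combined protocol and SAP*

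**What the plan says.** Section 8.B, under the Eosinophilic Esophagitis heading, sets the timing: "The questionnaire will be done at screening, then visits 4,6,9,10,11 and 12". The action follows: "those who have a score of 5 or more will be evaluated for possible Eosinophilic Esophagitis and will be referred to gastroenterology". It gives no deadline and does not mention dosing.

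Section 4.B, exclusion 2, bars participants with "Eosinophilic or other inflammatory (e.g. celiac) gastrointestinal disease". Section 4.C, item 3, makes EoE that develops on study a ground for withdrawal and says that participants who develop "symptoms compatible with Eosinophilic Esophagitis will be referred to a gastroenterologist". It does not ask for a pause in dosing.

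Section 5.D adds: "The screening visit may be combined with the initial escalation visit". The screening text in 5.D.1 says "We will determine if the patient is still eligible for the study, discuss the study and consent with the patient", then lists the examination, spirometry and optional tests. It does not mention the questionnaire. Under 5.D.2, a participant who tolerates 3 mg or 6 mg may start build-up on Day 2.

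At the other end of the study, 5.D schedules "a phone interview at 9 months and a final visit at the end of the study at 12 months" after the 6-month visit. Section 8.D has an adverse event evaluated until the earliest of resolution, medical stability or 30 days from its report. Section 4.D counts EoE together with severe non-anaphylactic product-related events. More than 3 such events suspend enrolment, escalation and build-up pending review by the data safety monitoring board (DSMB).

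**The concern.** The plan screens for symptoms of a disease that it excludes, but does not tie the result to the start of treatment. If score and first dose fall on the same day, the evaluation can only report after dosing has begun. Two things are at stake. First, a participant who may have excluded disease takes the allergen daily while the answer is pending. Second, EoE confirmed some weeks into dosing is hard to class as pre-existing or new, yet 8.C asks for a judgement of relatedness and 4.D counts the event. The baseline matters more here because entry is restricted to "Subjects who have completed an immunotherapy trial for peanut allergy within the last 18 months", so some entrants will have had recent active peanut therapy.

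The lesser matter is at the end of follow-up. The food stage has no clinic visit until the final one, when the compliance sheets are handed in. Symptoms noted after the 9-month call may therefore first reach staff at the final visit. A work-up opened there can outlast the 30 days in 8.D, with no later contact scheduled.

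**Working it through.** The plan states no figure on this point, so there is none to reproduce. The check is of sequence, followed by an illustration of size.

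**1. Shortest time from score to first dose.** Questionnaire at screening (8.B); screening and escalation may be one visit (5.D). The minimum interval is 0 days. None of 8.B, 5.D.1, 5.D.2, 4.B or 4.C states a hold for a score of 5 or more or for a pending work-up.

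**2. Upper illustration of exposure.** Inputs: the doses in Tables I and II, 14-day steps, no repeated step, no missed dose, no investigator action. The time to complete the evaluation is an assumption; the documents give none.

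- Day 1: 1.5 + 1.5 + 3 + 6 = 12 mg.
- Daily dose from Day 2: 6 mg; from Day 16: 12 mg; Day 30: 25 mg; Day 44: 50 mg; Day 58: 75 mg; Day 72: 100 mg; Day 86: 150 mg.
- Daily doses after Day 1, up to and including day T: T − 1.

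| Evaluation complete on day T (assumed) | Daily doses after Day 1 | Dose on that day | Cumulative, with Day 1 |
|---|---|---|---|
| 14 | 13 | 6 mg | 12 + 13×6 = 90 mg |
| 30 | 29 | 25 mg | 12 + 14×6 + 14×12 + 1×25 = 289 mg |
| 60 | 59 | 75 mg | 12 + 14×(6+12+25+50) + 3×75 = 1,539 mg |
| 90 | 89 | 150 mg | 12 + 14×(6+12+25+50+75+100) + 5×150 = 4,514 mg |

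**3. When the 30-day limit bites.** Let a work-up take W days, on an event reported d days before the final visit. If W ≤ 30, the result falls inside the required evaluation, which may run past the final visit. If W ≤ d, the diagnosis arises within the 12 months and can be entered as a new event. Only if W > 30 and W > d does recording depend on someone volunteering the result.

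During build-up, visits are at most 14 + 7 = 21 days apart, so a 30-day window contains at least one. In the food stage the scheduled contacts are at months 6, 9 and 12, about 91 days apart, and none follows month 12. The visit numbers in 8.B are not mapped to study time, but this step does not depend on them.

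**4. Reach into the stopping rule.** The rule needs 4 pooled events, so one unrecorded EoE changes the outcome only when the true count is exactly four. Timing limits it further. Assume even accrual over the full 24 months and a result 1.5 to 3 months after the month-12 visit. Enrolment is then still open for those who entered before month 24 − 13.5 = 10.5 or 24 − 15 = 9, that is 44% or 38% of entrants. Build-up lasts 16 weeks (about 3.7 months), so it ends by about month 27.7. For those who entered after month 27.7 − 13.5 = 14.2 or 27.7 − 15 = 12.7 (41% or 47%), both enrolment and build-up are over and only DSMB review could follow.

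**The case against.** The strongest reply is that the investigator already has the means to wait. Screening is where eligibility is determined (5.D.1). Exclusion 5 covers a significant gastrointestinal condition that puts the subject at risk, and 4.C, item 7, allows withdrawal for unacceptable risk. Section 6.A puts history and examination before any treatment at each visit. Section 8.D leaves the course of action after an event to the principal investigator, and 8.E requires procedures to be suspended if necessary. Combining the visits is optional. All of this stands, and it makes uninterrupted dosing with a known open referral less likely than the table implies. It remains discretion: none of these provisions names the score or sets an order.

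A reader might infer that the plan would dose people who have tested positive for EoE. The documents do not support that. The questionnaire is a symptom score used to monitor for the disease, the screening value also serves as a baseline, and no predictive value is given.

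A reader might also infer that late EoE diagnoses are lost, or take the share of study days near the final visit as the share of events lost. Neither follows. Section 8.D limits active evaluation but does not forbid recording, unsolicited complaints are a listed source of adverse events, and 4.D puts no time limit on EoE. Days are not events, and reports need not be spread evenly over them.

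Finally, the case report form, the diary and any procedure manuals are not in the supplied text, so an instruction to hold dosing could exist there.

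**Conclusion.** The main point holds as a gap in the written plan: a screening score of 5 or more triggers an evaluation that need not precede the first peanut dose, although the disease in question is an exclusion. The interval can be 0 days. The 13 to 89 further doses are an upper illustration that rests on assumed evaluation times and no investigator action. The number of participants affected cannot be estimated from the documents.

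The second point holds only in a narrow form. For a work-up that is opened near the final visit and lasts more than 30 days, active follow-up may end before the diagnosis, which may then go unrecorded and uncounted under 4.D unless someone reports it. Its effect on the stopping rule shrinks as enrolment and build-up finish. Neither point undermines the primary estimates.

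**What to change.** Main change, in 8.B and 5.D:

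- Score the screening questionnaire before the first escalation dose.
- At 5 or more, hold dosing until the evaluation that the plan already requires is complete. Confirmed EoE is then exclusion 2.
- Allow the combined screening and escalation visit only when the score is below 5.
- Judge the 18-month limit in inclusion 2 at the screening date, so that a hold does not make anyone ineligible.

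Minor change, in 8.D: exempt suspected EoE from the 30-day limit and follow it, by phone after the final visit if needed, to a recorded diagnosis that counts under 4.D.

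The cost is a sentence or two in each section, delayed dosing and a separate escalation visit for the unknown number who score 5 or more at screening, and a few calls after the final visit. There is a precedent within the plan: 8.A already follows pregnancies by phone every 3 months to delivery.

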5. PEANUT FOOD EQUIVALENT PHASE

At the end of maintenance peanut OIT phase, subjects will be given instruction during their last study visit in maintenance phase to start a peanut food equivalent of 300 mg peanut protein: which include the following options: peanuts (not dry roasted), peanut butter, powdered peanut butter, mini snickers, mini Reese's cup, cheese peanut butter crackers, Reese's pieces, Reese's peanut butter chips or Goober. An instruction sheet will be provided on how much to take of one of these products on a daily basis. This phase will last for 6 months. During this phase, subjects will continue to fill compliance sheets and they will receive phone calls from study coordinators at 9 months. This will be no study visits until the end of this phase to hand daily compliance sheets and fill a survey. At the end of the study the subjects may have the option to enroll in our peanut OIT follow up study if study investigator deemed they meet inclusion criteria for the study.

E. HANDLING ADVERSE REACTIONS AND FOLLOW UP DURING HOME DOSING

Each subject is given multiple ways to contact study staff when they are enrolled in the study. This is reviewed at the end of each visit. The families are told to contact the study staff if they have any questions or concerns before the next visit or at any time during the study. Study contact information given to families include the research clinic phone number, email addresses and office numbers of the, study coordinators, and instructions for how to get in contact with the pediatric on-call allergist who can reach the lead coordinator if needed. Subjects who have any symptoms during observed dosing, or those who express any specific concerns are given a follow up phone call on the day after dose escalation. All subjects will be asked to carry an auto-injector epinephrine. If prescription is not provided by their physician, we will provide them with a prescription for an auto-injector epinephrine. We will ask subjects to fill their prescription and

bring their epinephrine auto-injector with them before starting treatment to verify they have filled their prescription.

F. MANAGING MISSED DOSES

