For additional information and a printable version of the NCI-CTCAE manual, consult the NCI- CTCAE website,

<http://ctep.cancer.gov/reporting/ctc.html>.

D. ADVERSE EVENTS COLLECTION PROCEDURES

The Principal Investigator is responsible for collecting and recording all clinical data. As these results are collected, all toxicities and adverse events will be identified and reported as described above. The Principal Investigator will determine relationship of the event to the study activities and decide the course of action for the study participant.

Adverse events will be evaluated from the onset of the event until the time the event is resolved or medically stable or until 30 days after reporting of the event, whichever comes first.

Adverse events may be discovered through any of these methods:

1. Observing or questioning the participant during study visits.
2. Reviewing the forms given to the patient for home monitoring and documenting compliance.
3. Receiving an unsolicited complaint from the participant.

E. SERIOUS ADVERSE EVENT NOTIFICATION

The research staff will notify the principle investigator of any serious adverse event immediately on learning about the event. Serious adverse events will be recorded on the adverse event CRF within 24 hours of their occurrence. The following attributes must be assigned:

- Description
- Date of onset and resolution (if known when reported)
- Severity
- Assessment of relatedness to test procedure
- Action taken

The principal investigator must apply their clinical judgment to determine whether an adverse event is of sufficient severity to require that the subject be removed from treatment. If necessary, an investigator must suspend any trial procedures and institute the necessary medical therapy to protect a subject from any immediate danger.

Subsequent review by the DSMB or IRB may suspend further treatment or procedures. The DSMB retain the authority to suspend additional enrollment and treatments as applicable.

A subject may also voluntarily withdraw from the study due to what he/she perceives as an intolerable adverse event, or for any other reason. If

voluntary withdrawal is requested, the subject should be asked to complete a study termination form, and be given appropriate care under medical supervision until the symptoms of any adverse event resolve or their condition becomes stable.

F. NOTIFYING THE IRB AND DSMB

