Aim 2. Characterize and compare the two stages of the protocol in terms of safety and compliance.

We will rely on the following methods to accomplish Aim 2:

1. Our main analyses will focus on stage-specific estimates of incidence rates of adverse events and the proportion of days of treatment missed.

Comparisons of the two stages will rely on logistic regression models for rates, and generalized log-linear models for counts of days. The primary emphasis will be on point estimates and confidence interval estimates. No hypothesis tests will be performed.

2. Our secondary analyses will include estimation of

- the stage-specific incidence rates of gastrointestinal AEs during the entire 2-stage treatment sequence.
- the stage-specific incidence rates of Epipen use
- the stage-specific incidence rates of drop-outs due to gastrointestinal AEs.

Comparisons of the two stages will rely on logistic regression models for rates, and generalized log-linear models for counts of Epipen usages. The primary emphasis will be on point estimates and confidence interval estimates. No hypothesis tests will be performed.

3. Exploratory analyses will be used to investigate potential candidate risk factors for AEs (using logistic regression models) and causes of missed treatment days (using generalized log-linear models for counts of days).

4. Descriptive tabular and graphical methods will be used to visualize the data and examine the relationships among the measures of interest using graphical and descriptive methods.

Statistical estimates of interest include stage-specific parameter estimates (e.g., incidence rates) as well as estimates of differences between stage-specific parameters (e.g., odds ratios, or rate differences). All statistical estimates will be tabulated with the corresponding 95% confidence intervals (CI). Interpretation of these CIs will be an integral part of analysis. For Aim 2, sensitivity analyses will be performed to evaluate the robustness of the main

results to reasonable perturbations of the choices of statistical methods and statistical assumptions used.

Aim 3. Explore the mechanisms responsible for long-term desensitization and/or tolerance to food allergens induced by immunotherapy.

We will rely on the following methods to accomplish Aim 3:

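### Adverse events are looked for harder in the flour stage than in the food stage, so Aim 2's all-source comparison of AE rates may favour food by an unknown amount

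*Combined protocol and SAP*

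**What the plan says.** Section 8.D lists three ways in which AEs may be discovered. The first is "Observing or questioning the participant during study visits"; the second, for events at home, is "Reviewing the forms given to the patient for home monitoring and documenting compliance"; and the third is "Receiving an unsolicited complaint from the participant". Section 8.A defines an AE broadly, as any new or worsening undesirable event, related to the study or not.

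Visits are concentrated in the flour stage. Section 5.D sets an escalation visit, frequent up-dosing visits, then "a visit at the end of peanut OIT treatment at 6 months, a phone interview at 9 months", with the last visit at month 12. For the food phase, section 5.D item 5 says: "This will be no study visits until the end of this phase to hand daily compliance sheets and fill a survey". Section 5.E adds a next-day contact linked to dosing in clinic: "Subjects who have any symptoms during observed dosing, or those who express any specific concerns are given a follow up phone call".

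The home sheets run through both stages. Under section 6.F they record compliance, reactions, symptoms and treatment, and are handed in at each visit and at the end of the study.

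For Aim 2, section 10.B states: "Our main analyses will focus on stage-specific estimates of incidence rates of adverse events and the proportion of days of treatment missed". The stages are then compared by regression, with emphasis on point estimates and confidence intervals and without hypothesis tests. Nothing there restricts, adjusts or stratifies by how an event came to light. The sensitivity analyses are described only in general terms.

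**The concern.** A comparison of two AE rates is fair only if events are sought with similar effort on both sides. Here one stage has staff-observed doses, a history and physical examination at each visit (section 6.A), and sheets that can be queried within about two weeks during build-up. The other has a single call and a single closing visit. Events that a participant would mention only when asked, or that the sheet is not designed to hold, have more chances to be recorded on flour.

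Comparing the safety of flour and food is a stated purpose of the study (section 1.B and Aim 2). If detection is lower on food, part of a lower food-stage AE rate would reflect recording and not tolerability. The confidence interval around the comparison would not show this, because it covers sampling error only.

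**Working it through.** The plan gives no contact count and no capture rate, so there is no figure of its own to reproduce.

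**Step 1. Count the scheduled contacts after screening.**
- Flour: escalation 1 (section 5.D item 2) + Day 2 visit 1 + up-dosing visits 8 (Table II, doses 6 to 13) + end-of-OIT visit 1 = 11. The first 10 include observed dosing.
- Food: one visit (month 12) and one call (month 9).
- Section 5.D says: "The screening visit may be combined with the initial escalation visit". If it is not combined, it adds a visit before any dosing and leaves the count of 11 unchanged.
- Cross-check: the esophagitis questionnaire schedule in section 8.B runs to visit 12, which fits 11 + 1 if those numbers are visit numbers.

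**Step 2. Convert to contacts per month.**
- Flour at 6 months: 11/6 = 1.83 visits per month. Food: 1/6 = 0.17 visits, or 2/6 = 0.33 contacts with the call. Ratios: 11 and 5.5.
- Flour at 16 weeks plus 3 months (about 6.67 months): 11/6.67 = 1.65. Ratios: 9.9 and 4.95.

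**Step 3. Locate the imbalance.** Ten of the 11 flour visits are escalation or build-up. At 300 mg, flour maintenance has one visit in 3 months, or 0.33 per month, against 0.33 contacts per month on food (0.17 if only visits count). The gap in contact therefore lies almost wholly in build-up.

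**Step 4. Show what this could do to the rate ratio.** Suppose the true AE rates are equal. Let d be the share of events captured by sheet or spontaneous report, and v the share of the remainder recovered by staff questioning. Share recorded = d + (1 − d) × v. The documents give neither d nor v; all values below are assumptions.

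| d flour / food | v flour / food | Recorded, flour | Recorded, food | Apparent food:flour ratio |
|---|---|---|---|---|
| 1.0 / 1.0 | any | 1.00 | 1.00 | 1.00 |
| 0.9 / 0.9 | 0.5 / 0.2 | 0.95 | 0.92 | 0.97 |
| 0.9 / 0.9 | 0.8 / 0.2 | 0.98 | 0.92 | 0.94 |
| 0.8 / 0.8 | 0.8 / 0.2 | 0.96 | 0.84 | 0.88 |
| 0.6 / 0.6 | 0.8 / 0.2 | 0.92 | 0.68 | 0.74 |
| 0.9 / 0.8 | 0.8 / 0.2 | 0.98 | 0.84 | 0.86 |
| 0.8 / 0.6 | 0.8 / 0.2 | 0.96 | 0.68 | 0.71 |

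Example, fourth row: 0.8 + 0.2 × 0.8 = 0.96; 0.8 + 0.2 × 0.2 = 0.84; 0.84/0.96 = 0.875. The last two rows let sheet capture fall on food, where sheets are handed in once after six months.

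**Step 5. Ask whether the sheets level the stages.** They help, but the text does not show that they suffice. They are described as recording dosing, reactions, symptoms and treatment, which is narrower than the AE definition. They also return about every two weeks in build-up but only once on food, so gaps cannot be queried promptly there.

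**The case against.** The food stage is not unobserved. Two of the three routes in section 8.D operate in both stages, and the food phase also has the month 9 call and a closing survey, which section 6.F names as a source alongside the sheets. The diary in section 5.G asks for symptoms and side-effects of daily dosing. Observed dosing covers about 10 of some 180 flour days (10/180 = 5.6%); the other days rely on the same kind of home record as food. A reaction to a clinic dose is also a real event, not extra detection. The comparison is secondary, uncontrolled and estimation-only. All of this stands, and it limits the size of the effect.

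Three stronger readings are tempting and not supported:
- A reader might infer that 11 visits against 1 measures the bias. It measures contact, not detection, and with complete sheets the bias is nil.
- A reader might infer that the month 9 call does not ask about AEs. Section 8.D does not list it, but its wording is permissive and the call script is not in the text, so this cannot be known.
- A reader might infer that sheet-recorded home-day events should become the main comparison. That would remove the escalation day and the first dose at each new level from the flour rate. It would discard real reactions and change what Aim 2 estimates.

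What remains is that the plan neither records the detection source nor examines its effect.

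**Conclusion.** The point holds as a possible tilt of unknown size. Detection effort differs by stage by design, the direction favours food, and Aim 2 has no step that would reveal it. Under the assumed capture rates tabulated above, equal true rates would appear as food:flour ratios from 0.97 down to 0.71, and as 1.00 if the sheets are complete. Mild events and events unrelated to dosing are most exposed; SAEs and epinephrine use less so.

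A reader might go further and infer that any lower food-stage rate would be an artefact. The documents do not support that. Real up-dosing reactions, and the fact that only participants judged qualified move to food, would also lower the food-stage rate; these are separate from detection. The conclusion rests on the visit schedule as written, with no repeated or extra visits, and on sheets being less than complete. The overall Aim 1 rate does not depend on the stage contrast.

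**What to change.** 1. Add a source-of-detection field to the AE form: observed dose, visit questioning, home sheet, call, survey or unsolicited report. This is hard to reconstruct later, so it should be collected prospectively.
2. List the existing month 9 call in section 8.D as an AE source, and ask the same AE questions on it as at visits.
3. Keep the all-source stage comparison in section 10.B, Aim 2. Pre-specify beside it a comparison restricted to sheet-recorded events on home-dosing days, for the full stages and again for 300 mg flour maintenance against food. Tabulate observed-dose and visit-elicited events separately.
4. State that a lower food-stage AE rate will not be reported as a safety advantage unless the restricted comparison agrees.

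The cost is one CRF field, a slightly longer call, a few lines of analysis plan, and wider confidence intervals in the restricted comparison. Because that comparison omits real reactions to observed up-dosing, it supplements the all-source estimate and does not replace it. It also leaves some imbalance in how often sheets are returned; the maintenance-against-food version is the closest match on scheduled contact.
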